6.6.1 Primary Effectiveness Endpoints and Analyses

Primary endpoints of this study are pain reduction and functional improvement. Pain reduction will be assessed by using VAS pain score and functional improvement will be assessed by using MSTS score. The pain VAS is a single-item scale. It is assessed on scale range from 0-100mm with 0 means “no pain” and 100 means “pain as bad as it could be” or “worst imaginable pain”. MSTS score is a six-item scale. It ranges from 0-30. Higher score is associated with better function.

6.6.1.1 Pain Reduction

The primary effectiveness hypothesis concerning VAS pain improvements is:

H_0 : Mean improvement in VAS at Day 90 \leq 53.8 [ie. 80% of reference (inferior)]

H_a : Mean improvement in VAS at Day 90 $>$ 53.8 [ie. 80% of reference (not inferior)]

Further information on the reference value can be found in protocol Section 6.3.

A mixed model repeated measures (MMRM) model will be executed for the dependent variable of “change from baseline at each visit”, with the categorical main effect of visit (Day 7-14, Day 30, Day 90) as the independent variable. From this model, the estimate of the mean change from baseline at Day 90 and its standard error, will be established, and from this a one-sample t-test will be generated to test the null hypothesis of interest at a one-sided 0.05 level of significance. The MMRM model will be estimated using a direct likelihood approach as implemented in the SAS procedure PROC MIXED. The model will include the baseline value of the score as an additional covariate. The model is designed not only to account for correlations among responses over time, but to use these correlations to implicitly impute missing values from the non-missing values. Inferences based on this approach are unbiased

under the assumption of MAR (missing at random) which is a more generally true assumption than MCAR (missing completely at random)⁷.

Unless otherwise specified, the MMRM will have the following characteristics:

- All subjects in the ITT analysis set will be included in the primary effectiveness test as long as there are non-missing baseline and any post baseline (days 7-14, 30, and 90) values.
- The response variable will be the change VAS score from baseline to each post-baseline (days 7-14, 30, and 90) visit. Only post-baseline measurements collected up until the day 90 visit will be considered response values.
- Repeated post-baseline measurements from each subject will be identified by subject identifier.
- Within-subject correlations will be modeled using an unstructured covariance matrix structure. In the unlikely situation that this model does not converge (i.e., the study has too few observations for the number of parameters estimated), the model will use a compound symmetry structure which assumes equal correlation for a subject's measurements, regardless of how far apart in time they were taken.
- The following covariate will be used in the models:
 - Visit as defined by visit windows
 - Baseline VAS pain score
- The following SAS statements will be employed:

```
proc mixed method=ml;
  class visit subjid;
  model CHGvas = visit baseVAS/ ddfm=kr;
  repeated visit / type=un subject=subjid r rcorr;
  lsmeans visit / diff adjust=GT2 adjsdf=row;
  lsmeans estimate visit "mean improvement in VAS at Day 90" 0 0 1/ lower
  testvalue=-53.8;
  ods output lsmeans=lsmeans;
run;
```

where the variable CHGVAS contains the change from baseline VAS score for that patient-visit, VISIT is a categorical variable which identifies the Day 7-14, Day 30, and Day 90 assessments, BASEVAS is the baseline VAS, and SUBJID is the subject ID.

Least square mean estimate for change of VAS from baseline to Day 90 will be obtained from LSMESTIMATE statement, along with its corresponding 95% confidence intervals. In case unstructured covariance structure dose not converge, use type=cs to replace type=un in repeated statement.

Baseline VAS values, observed VAS values, change from baseline values and percent change from baseline values at post-baseline visits will be summarized.

6.6.1.2 Functional Improvement

The primary effectiveness hypothesis concerning MSTS functional improvements is:

H_0 : mean improvement in MSTS at Day 90 \leq 23.7 [ie. 80% of reference (inferior)]

H_a : mean improvement in MSTS at Day 90 $>$ 23.7 [ie. 80% of reference (not inferior)]

The MMRM analysis and data summarization MSTS score will be similar to that described for the VAS pain score; for information on the reference value, please see protocol Section 6.3. Testing for pain reduction will be performed before the evaluation of the MSTS endpoint. Only if the null hypothesis of inferiority in mean VAS pain improvement is rejected at $p < 0.05$, will the co-primary endpoint MSTS functional improvement be similarly tested.

6.6.1.3 Subgroup Analyses

Whether subject has actual fracture or impending fracture of the target humerus is recorded on CRF page. A subgroup analysis of subjects who had actual fracture and impending fracture will be performed for VAS and MSTS based on the statistical methods specified for these primary effectiveness endpoints, see sections 6.6.1.1 and 6.6.1.2. Subgroup analyses with MSTS will be performed only if the null hypothesis of inferiority in mean VAS improvement is rejected.

6.6.1.4 Other Analyses

A MMRM model comparing mean VAS change from baseline to Day 90 visit between subjects with actual and impending fracture will be performed. The following SAS statements will be employed:

```
proc mixed method=ml;
  class visit fracture_type subjID;
  model CHGVAS = baseVAS visit fracture_type visit*fracture_type
  baseVAS*visit baseVAS*fracture_type/ ddfm=kr;
  repeated visit / type=un subject=subjID;
  lsmeans visit*fracture_type/ cl pdiff;
  ods output diffs=diffs lsmeans=lsmeans;
run;
```

where the variables CHGVAS, VISIT, BASEVAS, and SUBJID are the same as those in section 6.6.1.1. FRACTURE_TYPE is a categorical variable for pathological fracture types (Actual vs. Impending). Visit*fracture_type, baseVAS*visit, and baseVAS*fracture_type are the two-way interaction terms among VISIT, FRACTURE_TYPE and BASEVAS.

Least square mean estimates for change of VAS from baseline to each post-baseline visit for subjects with actual and impending fractures will be obtained from ODS table LSMEANS. The difference of mean change of VAS from baseline to each post-baseline between subjects with actual and impending fractures, the SE, 95% CI, and p value from t distribution will be obtained from ODS table DIFFS.

6.6.2 Secondary Effectiveness Endpoints and Analyses

6.6.2.1 Procedure- and Device-related Complication Rate

When there is device performance issue/Malfunction, the date and time period when issue occurred will be recorded on CRF. Time period can be “During device preparation”, “During device implantation”, or “Post-Implantation”. Date/Time, time period, and specific reason on device malfunction will be listed. The number and percentage of subjects who experience a procedure- or device-related complication by the day 90 visit will be presented along with the corresponding 95% binomial confidence interval. Subjects with more than one device malfunction will be counted only once. The percentage of subjects who experience the complications by the day 180 and 360 visits will also be summarized.

6.6.2.2 Duration of Index Procedure and Length of Hospital Stay

Date of surgery, start time and end time of procedure, date of admission, date of discharge, time of discharge are recorded on CRF. Duration of index procedure will be calculated as (End time of procedure - Start time of procedure) and summarized in hours. Length of hospital stay will be calculated as (Date of discharge - Date of admission) +1 and summarized in days. Duration of procedure and length of hospital stay during reoperation will also be summarized.

6.6.2.3 Return to Pre-fracture Mobility

Subject’s pre-fracture mobility (“independent ADLs” or “ADLs with assistance”) will be captured at Visit 1 as baseline mobility. At each post-baseline visit (Visits 2-7), subjects are asked whether they have returned to pre-fracture mobility in the index arm. Possible replies are “Yes” or “No”. Shift table from pre-fracture mobility to each post-baseline visit will be summarized using counts and percentages.

6.6.2.4 No Pain on Palpation

Pain on palpation (Yes/No/Not done) is collected at each visit along with Grade (Mild/Moderate/Severe) and whether the pain is clinically significant (Yes/No). This information will be summarized.

6.6.2.5 MSTS Upper Extremity Functional Outcome

The MSTS upper extremity functional score evaluates the functional status of patients with impending and actual fractures of the humerus. In the MSTS system, numeric values (0 to 5) are assigned to each of the six categories of pain, function, emotional, hand positioning, manual dexterity, and lifting ability. They give a total score of between 0 and 30 with 0 indicating poor and 30 good. The total MSTS score will be recorded on CRF. It will be divided by 30 and multiplied by 100 to facilitate interpretation.

Baseline values, observed values, change from baseline values, and percent change from baseline values at post-baseline visits, will be summarized.

6.6.2.6 Range of Motion

At each visit, five tests for range of motion are performed: Flexion, Extension, Abduction, Lateral Rotation, and Medial Rotation. For each test, active and passive range of motion values are collected for both affected arm and unaffected arm. The observed test values range from 0 to 180, 0-180, 0-180, 0-100, 0-120 degrees for flexion, extension, abduction, lateral rotation, and medial rotation tests, respectively. Subjects will be classified into different categories based on the change of range of motion values from baseline: <0, >=0 and <=10, 11-20, 21-30, 31-40, 41-50, 51-60, 61-70, 71-80, 81-90, 91-100, degrees. The last category for flexion, extension, abduction, lateral rotation, and medial rotation tests are 171-180, 171-180, 171-180, 91-100, and 111-120, respectively. Number and percentage of subjects in each category will be summarized by visit and test. Range of motion test values, change from baseline values, and percent change from baseline values will be summarized by visit and test. Within each test the values will be summarized by active or passive and affected or unaffected arm.

6.6.3 Optional Analyses

All analysis and summaries listed in this section will be performed in ITT population. Data identified in this section will be displayed in subject listings.

6.6.3.1 Fracture Location/Type of Primary Cancer

Analysis of primary effectiveness endpoints as described in Sections 6.6.1.1 and 6.6.1.2 will be performed on subgroups in addition to those described in Section 6.6.1.3. These subgroups will be defined by fracture location and by type of primary cancer. Fracture location is recorded on CRF page with three categories: proximal, diaphyseal, and distal fractures. CRF recorded primary cancer type will be grouped into different categories based on the MedDRA High Level Group Terms (HLGT).

6.6.3.2 Activities of Daily Living Score

The activities of daily living will be assessed by EORTC-QLQ-BM22, which is a 22-item questionnaire assessment composed of multi-item measures. It has been divided into the following categories: Painful Sites (PS), Pain Characteristics (PC), Functional Interference (FI), and Psychosocial Aspects (PA) (Table 1).

Table 1. EORTC QLQ-BM22 Scales

Scale Name	Number of Items	Items Numbers	Item Range
Symptom scales			
Painful Sites (PS)	5	1-5	3
Pain Characteristics (PC)	3	6-8	3

Functional scales			
Functional Interference (FI)	8	9-16	3
Psychosocial Aspects (PA)	6	17-22	3

Range is defined as the maximum and minimum scale values for a particular item. Since all items in BM22 questionnaire have maximum of 4 and minimum of 1, the range for all items are 3. All of the scales will be transformed to range in score from 0 to 100. A high score for the symptom scales represents a high level of symptomatology or problems, whilst a high score for the functional scales represents a high level of functioning.

With regards to the positive phrasing of questions 21 and 22, the scoring must be reversed prior to statistical analysis.

The detailed scoring procedure for the EORTC QLQ-BM22 is outlined below:

PS: Painful Sites Scale (items 1-5)

- Compute the raw score (mean scale score) if at least 3 of the items have a valid score.
XPS = Mean of (Q1 – Q5)
- Carry out a linear transformation to convert to a 0-100 scale: $PS = \{(XPS - 1) / 3\} * 100$
- If fewer than 3 of the items have a valid score treat the scale as missing.

PC: Painful Characteristics Scale (items 6-8)

- Compute the raw score (mean scale score) if at least 2 of the items have a valid score.
XPC = Mean of (Q6 – Q8)
- Carry out a linear transformation to convert to a 0-100 scale: $PC = \{(XPC - 1) / 3\} * 100$
- If fewer than 2 of the items have a valid score treat the scale as missing.

FI: Functional Interference Scale (items 9-16)

- Compute the raw score (mean scale score) if at least 4 of the items have a valid score.
XFI = Mean of (Q9 – Q16)
- Carry out a linear transformation to convert to a 0-100 scale: $FI = \{1 - (XFI - 1) / 3\} * 100$
- If fewer than 4 of the items have a valid score treat the scale as missing.

PA: Psychosocial Aspects Scale (items 17-22)

- Reverse observed score for item 21-22 by 5 subtracted by Q21 or Q22
- Compute the raw score (mean scale score) if at least 3 of the items have a valid score.
XPA = Mean of (Q17 – Q22)

- Carry out a linear transformation to convert to a 0-100 scale: $PA = \{1 - (XPA - 1) / 3\} * 100$
- If fewer than 3 of the items have a valid score treat the scale as missing.

Observed values and changes from baseline for the EORTC-QLQ-BM22 two symptom scales (PS, PC) and two function scales (FI, PA) will be summarized by visit.

6.6.3.3 Assessment of Post-Surgery Physical Therapy, Supportive Orthopedic Device and Analgesic Medication Use

At surgery visit and each post-surgery visit, subjects are asked whether physical therapy, supportive orthopedic device, or analgesic medication is prescribed. The possible answers for physical therapy and supportive orthopedic device are “Yes” or “No”. The possible answers for analgesic medication are “None”, “Over-the-counter”, and “Prescription”. At each post-surgery visit, subjects are asked whether they completed physical therapy, supportive orthopedic device, or take analgesic medication since last visit. The possible answers are the same as at surgery visit. The prescription status for physical therapy, supportive orthopedic device, and analgesic medication at surgery and each post-surgery visit will be summarized using counts and percentages. Subjects who are prescribed with “Over-the-counter” or “Prescription” for analgesic medication will be counted as “Yes” to receive analgesic prescription at each visit.

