### **Stabilization Practices for Impending and Actual Pathological Fractures**

The goals of surgical treatment for impending and actual pathological fractures secondary to MBD are to relieve pain, reduce the need for narcotics, restore skeletal strength, and regain the ability to perform activities of daily living. Long bone surgical stabilization techniques are heavily dependent upon the location and extent of bone erosion, but may be broadly divided into methods employing intramedullary nails with locking pins and screws; extramedullary plates and screws; total joint arthroplasty; or via the direct injection of cement (with or without supplemental hardware stabilization).

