## **4 Risks and Benefits**

### **4.1 Anticipated Clinical Benefits**

Compared to traditional impending fracture or fracture treatment technologies, subjects may benefit from participating in this study as use of the IlluminOss PBSS will likely result in: (1) shorter operative time; (2) shorter length of hospital stay; (3) fewer narcotic and physical therapy prescriptions; and (4) fewer post-operative complications. Additionally, subjects may benefit from regaining use of their limb earlier than if they were treated with conventional plates, IM rods, or cement alone. It is also possible that subjects may not experience any of these benefits. The results of this study will benefit the medical community treating actual and impending pathological fractures secondary to metastatic bone disease by evaluating the safety and performance of the PBSS.

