### **6.1.2 Secondary Endpoints**

The secondary endpoints, evaluated at the Day 90 Visit, include:

- The individual components of the safety endpoint
- Other secondary endpoints include:
  - Duration of index procedure and length of hospital stay
  - Activities of Daily Living score through all follow-up intervals
  - Disability status
  - Evaluation of duration of physical therapy prescription
  - Assessment of prescription and over-the-counter analgesic medication use
  - Survivability from time of index procedure to death

The safety endpoints evaluated through Day 90 also include:

1. Incidence and number of AEs.
2. Incidence and number of procedure- and device-related complications.

The secondary endpoints and safety endpoints listed above will also be examined during the extended follow up portion of the trial at Day 180 and 360.

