#### **7.9.2 Health Economic Data**

Descriptive statistics for the duration of physical therapy prescription will be presented. The number and percentage of subjects who used supportive orthopedic devices post-surgery and who used prescription and over-the-counter analgesic medication will be presented. No formal statistical testing will be undertaken and no p-values will be presented.

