6.5 Concomitant Medication/Procedures

Concomitant medication and concomitant procedures are collected at each visit. Medications taken for a surgical procedure should also be included as concomitant medication.

All concomitant medications and concomitant procedures will be listed as recorded on CRF.

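### SAP 6.6.3.3 pools over-the-counter with prescription analgesics under a prescription label, so the planned summary cannot show moves between the two

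*SAP*

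**What the plan says.** SAP 6.6.3.3 describes two CRF items on analgesics. One, asked at surgery and at every later visit, is whether an analgesic is prescribed. The other, asked at post-surgery visits, is whether the subject has taken an analgesic since the last visit. For the first item, "The possible answers for analgesic medication are" none, over-the-counter and prescription; the second uses the same answers.

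The section then sets the tabulation. Prescription status "at surgery and each post-surgery visit will be summarized using counts and percentages". The only derivation rule given for analgesics follows: a subject with either the over-the-counter or the prescription answer counts as a yes "to receive analgesic prescription at each visit".

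The protocol names both types. The secondary endpoint in Protocol 6.1.2 (repeated in the synopsis) reads "Assessment of prescription and over-the-counter analgesic medication use". Protocol 7.9.2 says that the number and percentage of subjects "who used prescription and over-the-counter analgesic medication will be presented".

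Elsewhere in the SAP these data appear only in listings. On medications, Section 6.5 says "All concomitant medications and concomitant procedures will be listed as recorded on CRF", and Section 6.6.3 sends its own data to subject listings. Section 9, item 2, points to 6.6.3.3 for the health economic data and does not mention the pooling.

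**The concern.** The rule turns a three-level answer into yes or no and draws the line between none and everything else. The label, however, speaks of a prescription, and one of the two pooled answers is itself called Prescription. A reader of the table would naturally take the percentage as the share of subjects on prescription analgesics, when it is the share with any analgesic.

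At stake is one reported secondary result. The protocol names prescription and over-the-counter drugs side by side, and the CRF collects them separately. The planned summary drops that information, and no other specified table restores it. A shift towards prescription drugs and a shift away from them would both go unseen.

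**Working it through.** The plan gives no figure to reproduce. The check is the effect of the coding rule, followed by a search for another output that would fill the gap.

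**Effect of the rule.** At a visit with N non-missing answers (SAP 4.1 bases percentages on non-missing values), let P, O and Z be the numbers answering prescription, over-the-counter and none, so that P + O + Z = N.

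- Planned row: Yes = (P + O) / N.
- If k subjects move from prescription to over-the-counter: Yes = ((P − k) + (O + k)) / N = (P + O) / N, which is unchanged.
- The prescription percentage changes by −k / N. For a move the other way the sign is reversed, and Yes is again unchanged.
- Apart from a change in who contributes an answer, only a move to or from none alters the row.

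This holds for any counts.

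**Illustration.** The documents give no analgesic counts, so these are assumptions. N = 80 is the planned enrolment, held fixed at both visits for simplicity.

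| Prescription status | Surgery | Day 90 |
|---|---|---|
| Prescription | 60 (75.0%) | 20 (25.0%) |
| Over-the-counter | 10 (12.5%) | 50 (62.5%) |
| None | 10 (12.5%) | 10 (12.5%) |
| Planned Yes row | 70 (87.5%) | 70 (87.5%) |

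Here k = 40 and the hidden change is 40/80 = 50 percentage points. From the same starting counts, k can run from 0 to 60, so the hidden fall can be anything from 0 to 60/80 = 75 points. In the other direction, if all 10 over-the-counter subjects moved to prescription, prescription status would rise from 75.0% to 70/80 = 87.5%, and the Yes row would still read 87.5%.

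**Other outputs.**

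- SAP 6.5: concomitant medications are listed, with no summary table.
- SAP 6.6.3: the three-level answers appear in subject listings.
- SAP 6.6.3.3: the tabulation sentence covers prescription status. No tabulation is stated for analgesics taken since the last visit, although Protocol 7.9.2 is worded in terms of subjects who used them.

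No specified table separates the two types.

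**The case against.** The best defence is that the text does not forbid a three-level table. SAP 4.1 says in general that all categories of a categorical variable are shown, and the pooled yes could be an extra row. That reading is possible but not secure. The specific rule in 6.6.3.3 redefines the reported status as yes or no, and no three-level table is specified. A programmer who follows the section as written would produce the pooled percentage.

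It can also be said that the protocol asks for little. Protocol 7.9.2 sits under optional analyses, excludes formal testing and does not require separate rows; Protocol 6.1.2 names both types without asking for a contrast. This stands, and it limits the weight of the point. It does not justify a prescription label on a figure for any analgesic.

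Four stronger readings are tempting, and the documents do not support them:

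- *Over-the-counter use is miscounted.* The pooling rule covers what is prescribed. No pooling is stated for what was taken since the last visit. Over-the-counter is also a permitted answer to the prescribed item, so the yes may be loose wording for any analgesic advised.
- *The table defeats a test of the narcotic benefit.* Protocol 4.1 does anticipate "fewer narcotic and physical therapy prescriptions", but in comparison with traditional treatments. The study has no comparator, so neither the planned table nor a better one could test that. Prescription is also not the same as narcotic.
- *The VAS result is compromised.* The primary model does not use this variable, and cross-tabulating analgesic status with VAS change would be a new exploratory analysis that this point does not need.
- *Data are lost.* They are collected and listed; only the summary lacks them.

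**Conclusion.** The point holds as a defect of labelling and table design in a descriptive secondary endpoint. Followed as written, SAP 6.6.3.3 reports any analgesic as an analgesic prescription, and its percentage cannot respond to a switch between prescription and over-the-counter drugs.

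The insensitivity follows from the rule and needs no assumption about counts. How much would be hidden in this trial cannot be known from the documents; the 50 points above are only an illustration. The conclusion assumes that the pooling rule governs the table and is not an addition to a three-level display. The primary analysis, power and alpha are unaffected. The priority is low, but the correction is nearly free.

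**What to change.** In SAP 6.6.3.3, replace the pooling rule with a table of counts and percentages for none, over-the-counter and prescription at surgery and each later visit. State that analgesics taken since the last visit will be tabulated in the same three levels at each post-surgery visit. If a pooled row is kept, label it as any analgesic.

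The cost is one table layout, repeated for the second item, and a few sentences in the SAP. The CRF already collects the answers, so no new data are needed.
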